APPENDIX B. TOXICITY GRADING SCALE FOR INJECTION SITE REACTIONS

Local Reaction to Injectable Product	Mild (Grade 1)	Moderate (Grade 2)	Severe (Grade 3)	Potentially Life Threatening (Grade 4)
Pain	Does not interfere with activity	Repeated use of non-narcotic pain reliever > 24 hours or interferes with activity	Any use of narcotic pain reliever or prevents daily activity	Emergency room (ER) visit or hospitalization
Tenderness	Mild discomfort to touch	Discomfort with movement	Significant discomfort at rest	ER visit or hospitalization
Erythema/Redness ^a	2.5-5 cm	5.1-10 cm	> 10 cm	Necrosis or exfoliative dermatitis
Induration/Swelling ^b	2.5-5 cm and does not interfere with activity	5.1-10 cm or interferes with activity	> 10 cm or prevents daily activity	Necrosis

^a In addition to grading the measured local reaction at the greatest single diameter, the measurement should be recorded as a continuous variable.

[figure not shown]
^b Induration/swelling should be evaluated and graded using the functional scale as well as the actual measurement.

APPENDIX C. INJECTION SITE ASSESSMENT FORM

Injection Site Assessment				
Nominal Time Point: _____		Time of Assessment: ____:____		
Injection Site Location (circle one): Right Thigh Left Thigh				
Local Reaction	Severity (circle one)		Comments	Staff Initials
Injection Site Pain	None	Mild	_____	
	Moderate	Severe	_____	
	Potentially Life Threatening		_____	
Tenderness	None	Mild	_____	
	Moderate	Severe	_____	
	Potentially Life Threatening		_____	
Erythema/ Redness	None	Mild	_____	
	Moderate	Severe	_____	
	Potentially Life Threatening		_____	
Induration/ Swelling	None	Mild	_____	
	Moderate	Severe	_____	
	Potentially Life Threatening		_____	
SEE APPENDIX B: Toxicity Grading Scale for Injection Site Reactions				
Mild = Grade 1, Moderate = Grade 2, Severe = Grade 3, Potentially Life Threatening = Grade 4				

APPENDIX D. RICHMOND AGITATION AND SEDATION SCALE (RASS)

Score	Term	Description
+4	Combative	Overtly combative, violent, immediate danger to staff
+3	Very agitated	Has aggressive behavior toward staff
+2	Agitated	Frequent non-purposeful movement
+1	Restless	Anxious but movements not aggressive vigorous
0	Alert and calm	
-1	Drowsy	Not fully alert, but has sustained awakening (eye-opening/eye contact) to voice (>10 seconds)
-2	Light sedation	Briefly awakens with eye contact to voice (<10 seconds)
-3	Moderate sedation	Movement or eye opening to voice (but no eye contact)
-4	Deep sedation	No response to voice, but movement or eye opening to physical stimulation
-5	Unarousable	No response to voice or physical stimulation

Procedure for RASS Assessment

1. Observe patient
 - a. Patient is alert, restless, or agitated Score 0 to +4
2. If not alert, state patient's name and say to open eyes and look at speaker.
 - b. Patient awakens with sustained eye opening and eye contact. Score -1
 - c. Patient awakens with eye opening and eye contact, but not sustained. Score -2
 - d. Patient has any movement in response to voice but no eye contact Score -3
3. When no response to verbal stimulation, physically stimulate patient by shaking shoulder and/or rubbing sternum
 - e. Patient has any movement in response to voice but no eye contact. Score -4
 - f. Patient has no response to any stimulation Score -5

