11.1.5. Physical Examination

Each subject will have a complete physical examination at screening, Day -1, and Day 8. Abbreviated (targeted) physical examinations will be performed as needed prior to dosing on Day 1 and prior to discharge on Day 3. A complete physical examination includes all major systems, including general appearance, EENT, chest/respiratory, heart/cardiovascular, abdomen/gastrointestinal, lymph nodes/spleen, genitourinary, musculoskeletal, skin, neurological, and hepatic. The screening physical exam includes an assessment of upper leg

muscle tissue (ie, adequacy of tissue for IM injection). Targeted physical examinations may be performed at other times as deemed necessary by the investigator.

In addition, at the request of the DSMB for Cohorts 3-5, a brief neurological assessment will be performed at 1 hour post dosing (+30 min) on Day 1 to assess alertness/level of consciousness, orientation, ability to follow commands and coordination. The assessment will be documented in the subject's medical record. At the end of each cohort, the PI will provide narratives (per cohort and subject) for inclusion in the DSMB data reviews.

The brief neurological assessment will be performed as follows in this sequence:

- 1) To assess alertness and level of consciousness, the RASS ([Appendix D](#)) will be employed and the completed scale will be added to the subject's medical record.
The RASS score will be entered into the eCRF; however, the scores for orientation and ability to follow commands (see below) will not be entered into the eCRF.
- 2) Orientation will be assessed using questions 1 and 2 of the Folstein Mini-Mental Status Examination ([Rovner and Folstein, 1987](#)), as shown below. The answers to each question will be noted in the subject's medical record, along with the combined score for the two questions. Scoring will be performed according to Rovner and Folstein ([1987](#)).
 - “What is the year? Season? Date? Day of the week? Month?”
 - “Where are we now: State? County? Town/city? Hospital? Floor?”
- 3) Ability to follow commands and coordination (to the extent possible) will be assessed using a modified question 8 of the Folstein Mini-Mental Status Examination as shown below. The total score will be noted in the subject's medical record. Scoring will be performed according to Rovner and Folstein ([1987](#)).
 - “Take the paper in your right hand, fold it in half, and hand it back to me.”

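### Protocol Appendix D: RASS step 3e (-4) cannot be met as worded, so the procedure has no line for a subject who responds only to physical stimulation, contrary to the -4 row of its own table

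*Protocol*

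**What the plan says.** Protocol Appendix D has two parts, a score table and a numbered procedure.

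- **Table, -3 row:** "Movement or eye opening to voice (but no eye contact").
- **Table, -4 row:** "No response to voice, but movement or eye opening to" physical stimulation.
- **Procedure, step 2d:** "Patient has any movement in response to voice but no eye contact Score -3".
- **Procedure, step 3 (entry condition):** "When no response to verbal stimulation, physically stimulate patient by shaking shoulder and/or rubbing sternum".
- **Procedure, step 3e:** "Patient has any movement in response to voice but no eye contact. Score -4".
- **Procedure, step 3f:** "Patient has no response to any stimulation Score -5".

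The appendix is a working instrument. Protocol 11.1.5 states that "at the request of the DSMB for Cohorts 3-5, a brief neurological assessment will be performed at 1 hour post dosing", names the Appendix D RASS as its first component, and adds that "The RASS score will be entered into the eCRF". The scores for orientation and for following commands stay in the medical record. The same section has the PI supply narratives for the DSMB data reviews at the end of each cohort. Protocol 11.1.6 and 11.3.1 also use the Appendix D scale to grade the severity of agitation and sedation adverse events, in any cohort.

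**The concern.** Steps 2d and 3e describe the same response in the same words and give it different scores. Step 3e also contradicts the condition under which step 3 is entered. It reads as a line copied from step 2d and not adapted to physical stimulation.

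The -4 level should identify a subject who no longer responds to voice but still responds to shaking or a sternal rub. A rater who works through the numbered steps finds no line for that subject. Different raters could then record -4 (from the table), -5 (the only other line in step 3), or -3 (from the matching words in step 2d).

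Sedated scores are a foreseeable use of the form. Protocol 5.3.1.2 lists drowsiness as usual at the low end of the dose range and loss of consciousness as possible. What is at stake is whether one category of a safety scale is recorded consistently.

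**Working it through.** No arithmetic applies to the defect itself. The check sets the table against the procedure for each level of sedation, and then traces where the score is used.

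**Step 1. Map each response to a score.**

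| Response of a subject who is not alert | Table | Procedure |
|---|---|---|
| Sustained eye contact to voice | -1 | -1 (2b) |
| Brief eye contact to voice | -2 | -2 (2c) |
| Movement to voice, no eye contact | -3 | -3 (2d) |
| No response to voice; response to physical stimulation | -4 | no line that can be met |
| No response to voice or physical stimulation | -5 | -5 (3f) |

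The two parts agree at -1, -2, -3 and -5. They disagree at -4 only.

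**Step 2. Test whether step 3e can be reached.** The steps are sequential. A subject who moves to voice without eye contact is scored -3 at step 2d and does not enter step 3. A subject who enters step 3 has, by its entry condition, not responded to voice. Step 3e requires a response to voice. No subject satisfies both, so 3e is an empty category.

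**Step 3. Find who is left without a line.** A subject who enters step 3 and moves when shaken fails 3e (no response to voice) and fails 3f (there was a response to stimulation). This is the only group with no score under the procedure.

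**Step 4. Trace the use of the score.**

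- *eCRF and DSMB (Protocol 11.1.5):* routine at 1 hour post dose in Cohorts 3-5, within the assessment that the DSMB asked for.
- *Adverse event severity (Protocol 11.1.6, 11.3.1):* sedation events in any cohort.
- *DLT criteria (Protocol 7.6.1.1, 7.6.1.2) and Table 6:* no criterion uses a RASS score.
- *Rescue (Protocol 9.2.1):* the RASS criterion is on the agitation side of the scale only; sedation scores play no part.
- *Analysis (Protocol 12.1.2; SAP 6.14.6):* RASS is summarised descriptively. It is in none of the 110 tests in SAP 6.3, Table 7.

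**Step 5. Size.** Cohorts 3-5 hold 3 × 8 = 24 to 3 × 12 = 36 subjects, of whom 3 × 6 = 18 to 3 × 9 = 27 receive active drug. That is the number assessed routinely. The number affected is the subset at the -4 level, plus any such subject graded for a sedation event in Cohorts 1-2. The documents give no expected frequency for that level.

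**The case against.** The strongest reply is that the appendix resolves itself. The table directly above the procedure defines -4 without ambiguity. At step 3 the rater has just applied physical stimulation and chooses between -4 and -5; if the subject moves, 3f is excluded by its own words and the table supplies -4. Protocol 11.1.6 also requires experienced and trained staff for the RASS. This stands as a limit on likelihood: systematic mis-scoring is not to be expected. It does not remove the contradiction, because nothing in the appendix says whether the table or the procedure governs.

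Three stronger readings are tempting, and the documents do not support them.

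- *A voice-responsive subject can be scored either -3 or -4.* The duplicated wording invites this, but the sequence prevents it: that subject is scored at 2d and never reaches 3e.
- *The error falls at a level that drives escalation.* No DLT, cohort expansion, halting or rescue rule uses a sedation score. The DSMB sees the sedation information, together with the PI's narratives, but no threshold is attached to it.
- *Up to 36 subjects are affected.* That is everyone assessed routinely in Cohorts 3-5, including 6 to 9 on placebo. It is not the number at the affected level.

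**Conclusion.** The concern holds as an internal contradiction in a scoring instrument that is in use. Step 3e conflicts with its own entry condition and with the -4 row of the table, and the procedure therefore has no line for a subject who responds only to physical stimulation.

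Its reach is narrow. Directly affected are subjects at that one level, in a number that the documents do not give. The consequence is possible inconsistency in descriptive RASS data, in sedation severity grades in any cohort, and in the Cohort 3-5 sedation information for the DSMB. With 6 to 9 active subjects per cohort, a single misclassified subject would be visible in a dose-group summary. No test result, DLT count, rescue criterion or stopping rule depends on it.

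This rests on two assumptions: that raters take the steps in order, and that the site worksheet reproduces Appendix D. If the worksheet already carries the table's -4 definition in step 3e, only the protocol text needs correction.

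**What to change.** Reconcile step 3e with the -4 row of the table in the same appendix, so that it refers to movement or eye opening on physical stimulation. The entry condition of step 3 already agrees with that row.

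Reissue the RASS worksheet and tell the raters. Check against source any -4 or -5 already recorded, and any -3 given after physical stimulation was applied.

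The cost is one line of the appendix, one reissued form and a source check confined to those scores. No change to the SAP is needed.

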ICH	International Conference on Harmonisation of Technical Requirements for Registration of Pharmaceuticals for Human Use
IM	Intramuscular
IND	Investigational New Drug
IV	Intravenous
Kg	Kilogram
L	Liter
MedDRA	Medical Dictionary for Regulatory Activities
Min	Minute
mL	milliliter
MRT	Mean Residence Time
PD	Pharmacodynamics
PI	Principal Investigator
PK	Pharmacokinetics
PR interval	Time between P and R waves
██████████	██████████
QRS interval	Time between Q, R, and S waves
QTc	QT interval adjusted for heart rate
QTcF	QTc (Fridericia)

RASS	Richmond Agitation Sedation Scale
SAE	Sever Adverse Event
SAP	Statistical Analysis Plan
Scop HBT	Scopolamine Hydrobromide Trihydrate
SD	Study Day
Sec	Second
SEM	Standard Error of the Mean
Ng	Nanogram
$t_{1/2}$	Half life
TEAEs	Treatment-emergent Adverse Events
T_{max}	Time to maximum concentration
VAS	Visual Analog Scale
V_d/F	Apparent Volume of Distribution
WHO	World Health Organization

Summary of Changes

Version	Change	Sections	Made By	Approved by
2.0	Updated personnel	Page 1-2	[REDACTED]	[REDACTED]
	Corrected typographical error	3.1	[REDACTED]	[REDACTED]
	Clarified references to protocol appendices	5.1.3.1 5.1.10	[REDACTED]	[REDACTED]
	Corrected references to other parts of the SAP	6.3	[REDACTED]	[REDACTED]
	Updated to clarify PK analysis will be presented in separate PK report	6.6.2	[REDACTED]	[REDACTED]
	Revised statistical modeling for PK parameters to better reflect the Protocol specified analyses.	6.3, 6.15	[REDACTED]	[REDACTED]
	Updated to add imputation rules for missing or partial dates for AEs and concomitant medications	6.6.3	[REDACTED]	[REDACTED]
	Updated to remove figures based on discussion and agreement from client Biostatistician. No figure shells will be provided.	5.1.9, 6.2 6.14.2, 6.14.3, 6.14.4, 6.14.6, 6.14.8, 6.18	[REDACTED]	[REDACTED]
	Add Table and Listing shells.	Table and Listing Shells	[REDACTED]	[REDACTED]

1. INTRODUCTION/BACKGROUND

This statistical analysis plan (SAP) describes the data analysis specifications for IND 130620; Protocol S-16-14 entitled “A Phase 1, Double-Blind, Randomized, Placebo-Controlled, Dose-Escalation Study to Evaluate the Safety, Tolerability, And Pharmacokinetics Of Intramuscular Administration Of Scopolamine Hydrobromide Trihydrate, Injection.” The preparation of this SAP adheres to the IRB-approved protocol S-16-14 version 2.0 dated March 12, 2020.

This SAP follows the International Conference on Harmonisation (ICH) Guidelines E3 and E9. In cases in which the analyses in this SAP differ from those in the study protocol, the analyses in the SAP supersede those in the protocol. Should differences exist, these will be described in Section 6.2 of this document.

This initial Phase 1 trial is a single, ascending dose study in healthy volunteers with single doses of Scopolamine Hydrobromide Trihydrate (Scop HBT) ranging from 0.005 to 0.021 mg/kg administered in a single intramuscular (IM) injection. The dosing regimen to be evaluated in future trials will be determined in part on the basis of the pharmacokinetic (PK) and safety data obtained in this Phase 1 study. All statistical analyses will be performed using SAS®, Version 9.4 or higher.

2. STUDY OBJECTIVES

The objectives of this study are:

- To characterize the safety and tolerability profile of ascending doses of Scop HBT administered by IM injection (0.005mg/kg to 0.021mg/kg), and set upper limits on the probability of extreme dose limiting toxicities and non-extreme DLTs across dosage levels;
- To characterize the PK of ascending doses of Scop HBT administered by IM injection, and assess dose-proportionality for C_{max} and AUC_{∞} , over the dosing range;

3. STUDY DESIGN

3.1 OVERVIEW AND LENGTH OF STUDY

This is a double blinded, placebo-controlled, Phase 1 sequential dose escalation study to evaluate the safety, tolerability, and PK of Scop HBT in healthy participants. Healthy volunteers will be assigned to one of five target dosage groups to receive Scop HBT or placebo, administered by IM injection. In each dosing cohort, the ratio of participants receiving placebo vs. active drug will be 1 placebo subject for every 3 active participants. Up to 60 participants will be enrolled.

Participants will be assigned, sequentially, to one of five escalating target dosage groups or to the placebo group beginning with the lowest dose first. New participants will not be enrolled into the next higher dose until at least eight participants in the previous dosing cohort have completed 8-day follow-up visits without the occurrence of DLTs, pre-defined as requiring termination of the study, and until approval by the data safety monitoring board (DSMB) following its review of the study data. Four additional participants, three active and one placebo, may be added to each cohort, depending upon AEs exhibited in the first eight participants.

The study drug or placebo will be administered IM into the anterior thigh using a consistent procedure. The dose will be based on the subject's weight. Treatment will begin at the lowest of

five Scop HBT target doses (0.005, 0.007, 0.011, 0.014, and 0.021 mg/kg) and progress to the next higher dosage escalating by multiples that range between 1.25 and 1.6 for each cohort. Escalation to the next dose level will only occur after safety has been determined by the DSMB in at least eight and up to twelve participants (of whom 6-9 will receive study drug), based on the clinical responses of the participants to each dosage level. Escalation will occur no sooner than six weeks after the first subject in each cohort has been dosed.

Participants will report to the study site on the day prior to scheduled dosing. On the day of dosing, ECG (3-5 lead) and vital signs (excluding body temperature) will be monitored continuously for 24 hours. Blood pressure (BP) will be evaluated and documented at specified times through the 48-hours post administration. Echocardiograms will be conducted at screening, baseline (Day -1), and at Study Days (SD) 1,2,3 & 8. Blood and urine samples for safety monitoring will be collected prior to dosing and according to a specified schedule through 48 hours post-dosing, as well as during the subject's return visit on SD 8. Blood and urine samples for PK analyses will be collected prior to dosing and according to a specified schedule through 24 hours post-dosing.

All participants will be observed as in-patients at the research center for the first 48 hours (post-dose) for AEs. Participants will also return for a study visit on SD 8 and receive a follow-up telephone call on SD 4 and SD 30. The study schedule of visits (time and events table) is presented in Section 3.2.

3.2 STUDY SCHEDULE (TIME AND EVENTS TABLE)

Table 1: Timeline of Key Events

Study Phase	Screening	Baseline ^a	Treatment ^a			Follow-up ^b		
			1 ^c	2 (24 ± 1 h)	3 (48 ± 1 h)	4 (+ 2 days)	8 (+2 days)	30 (+ 7 days)
Study Day	-30 to -2	-1						
Procedures								
Informed Consent	X							
Inclusion/Exclusion	X	X	X ^d					
Medical History	X	X						
Physical Examination	X	X	X ^e		X ^e		X	
Serum Pregnancy Test	X	X					X	
Laboratory Safety Tests ^f	X	X		X	X		X	
Serology ^g	X							
Urine Drug Screen ^h	X	X					X	
Alcohol Breathalyzer Test	X	X						
Body Weight and Height/Body Mass Index	X ⁱ	X ⁱ			X ⁱ		X ⁱ	
Vital Signs ^j	X	X	X	X	X		X	
Electrocardiogram (ECG), 12-lead (supine) ^k	X	X	X	X	X		X	

Study Phase	Screening	Baseline ^a	Treatment ^a			Follow-up ^b		
Study Day	-30 to -2	-1	1 ^c	2 (24 ± 1 h)	3 (48 ± 1 h)	4 (+ 2 days)	8 (+2 days)	30 (+ 7 days)
Procedures								
Dose Administration			X					
Pharmacokinetic Assessment			X ^d	X	X			
Adverse Events			X ^m	X	X	X	X	X
Prior/Concomitant Medications	X	X	X	X	X	X	X	X
Continuous Cardiovascular Monitoring			X ⁿ	X ⁿ				
Injection Site Assessment ^o			X	X	X		X	
Injection Site: VAS ^o			X	X	X		X	
Reminder of Study Restrictions	X				X	X	X	
Brief Psychiatric Rating Scale (BPRS) ^p	X	X	X		X		X	
Columbia-Suicide Severity Rating Scale (C-SSRS) ^q	X	X					X	
Richmond Agitation and Sedation Scale (RASS)			X ^r					
Structured Clinical Interview for DSM-5, Clinical Trial version (SCID-5-CT)		X ^s						
Digit Symbol Substitution Test ^t (DSST)	X	X		X			X	

^a Participants will be in clinic for the baseline and treatment days. Days 2 and 3 procedures should be performed at 24 and 48 hours (± 1 hour) post dose, respectively, except for PK samples, which should be collected as close to the specified time points as possible. Refer to [Table 2](#) for expansion of pre-dose through 36-hour post-dose activities.

^b Day 4 and Day 30 follow-up is conducted by telephone. Day 4 follow-up may be performed on Days 4-6. Day 30 follow-up may be performed on Days 30-37. Day 8 follow-up is an in-clinic visit and may be performed on Days 8-10.

^c See [Table 2](#) for study events occurring pre dose through 36 hours post dose.

^d Final eligibility criteria review and completion of eligibility checklist prior to dosing.

^e Abbreviated physical examinations with changes from Day -1 (baseline) noted; Day 1 exam is prior to dosing.

^f Hematology (including coagulation), serum chemistry, and urinalysis (refer to Section [5.1.6](#) for specific tests).

^g Fasting ≥ 8 hours at screening. Adequacy of venous access will be assessed and documented at screening.

^h Hepatitis B surface antigen, hepatitis C, HIV-1/2, and syphilis testing at screening only.

ⁱ Urine drug screen (refer to protocol Section [5.1.6](#) for specific tests).

ⁱ Body weight (kg) and height (cm; screening only) will be measured at screening and body mass index (BMI) calculated. Weight will be measured on Day -1 with BMI calculation. Day-1 weight to be used for Day 1 dose determination. Weight will be measured at Day 3 and Day 8 with no BMI calculation.

^j Systolic and diastolic blood pressure, heart rate, respiration rate, body temperature, and pulse oximetry will be performed after subject has been supine for at least 5 minutes. See [Table 2](#) for vital sign time points from pre dose through 24 hours post dose.

^k See [Table 2](#) for time points to performing ECG (supine) from pre-dose through 24 hours post-dose.

^l See [Table 2](#) for PK sample collection time points from pre dose through 36 hours post dose. PK samples should be collected as close to the actual time point as possible (within the windows specified in); however, when multiple tests are scheduled at the same time, ECG and vital signs will be performed within 5 minutes prior to the time point, and injection site and AE assessments will be performed immediately after the PK blood draw. AEs identified prior to dosing will be considered part of the medical history. Urine PK samples will be collected prior to dosing (no earlier than 2 hours pre-dose) and for 24 hours after dosing. All urine specimens will be pooled into 1 of 3 collection interval containers by the subject. See [Table 2](#) for collection intervals from pre-dose through 24 hours post dose.

^m See [Table 2](#) for AE assessment time points from pre dose through 24 hours post dose.

ⁿ Continuous cardiovascular monitoring of ECG (3-5 lead) and vital signs (blood pressure, heart rate, respiration rate, and pulse oximetry) from 1 hour prior to dosing through 24 hours post dose (see [Table 2](#))

^o Injection site assessments: Subject will be asked to rate the maximum intensity of pain, pruritus, tingling, and numbness using the VAS. See [Table 2](#) for assessment time points from pre dose through 24 hours post-dose. Immediately following the subjective assessment, an assessment of pain, tenderness, erythema, and induration at the injection site will be performed by a physician, physician assistant, or nurse.

^p See [Table 2](#) for assessment time points on Day 1. For items assessed over time (e.g., items 1, 2, and 3), the period of assessment should be “over the prior week,” except for the assessments performed at 6-8 and 48 hours post dose, which should be assessed “since the prior assessment.”

^q C-SSRS will be assessed at screening, Day -1 (baseline), and Day 8.

^r RASS will be used to assess severity only if AEs of general agitation or sedation occur.

^s SCID-5-CT will be administered at Day -1 to identify the presence of any major DSM-5 Axis I or II disorder.

^t The DSST will be administered at screening, baseline, 48 hours post dose, and Day 8 to detect any persistent cognitive impairment. The DSST will not be used to determine eligibility.

Table 2: Study Events Schedule – Pre-Dose through 36 Hours Post Dose

Activity/Assessment	Pre-Dose	Dosing = Time 0	Minutes Post-dose							Hours Post-dose									
			2	5	10	15	20	30	45	1	1.5	2	3	4	5	8	12	24	36
ECG	X			X	X	X		X	X	X	X		X		X	X	X	X	
Vital Signs	X			X	X	X		X	X	X	X		X		X	X	X	X	
Abbrev Physical Exam	X																		
Injection Site: VAS ^a	X			X	X	X		X	X	X	X		X		X	X	X	X	
Injection Site: Physician, Physician Assistant or Nurse	X			X	X	X		X	X	X	X		X		X	X	X	X	
BPRS ^b																	6		
C-SSRS																			
RASS																			
Final Eligibility	X																		
Eligibility Checklist	X																		
Randomization	X																		
Urine PK Samples	X																		
Blood PK Samples	X																		
Safety Lab Tests																			
Adverse Events	X																		
Concomitant Medications	X																		
Continuous Cardiovascular Monitoring	Begin																		
ECG (3-5 lead) & vital signs (blood pressure, heart rate, respiration rate, & pulse oximetry)																End			

^a If the PI or designee determines a subject is incapable of providing valid responses on the VAS or DSST due to the neuropsychiatric effects of Scop HBT, the reason(s) why the VAS assessment(s) could not be done will be documented by time point, and VAS or DSST assessments will be conducted once deemed subject is capable of providing responses.

^b BPRS will be performed at 6 (+ 2) hours post dose. The + 2-hour window is provided to allow the investigator some discretion, should he or she determine the assessment needs to be delayed. The timing may be dependent on the emergence and severity of neuropsychiatric symptoms.

